Exclusion criteria	Patients are excluded from the study if any of the following criteria apply:  1. Onset of HD symptoms prior to age of 21 years, corresponding to juvenile forms of HD.
	2. HD patients presenting rigid akinesia.
	3. Use of other vesicular monoamine transporter type 2 (VMAT2) inhibitors such as tetrabenazine, deutetrabenazine, or valbenazine within 3 months before enrollment, and at any time during the study period; and use of other antichoreic treatment such as any neuroleptic within 2 months or amantadine, memantine, riluzole within 1 month before enrollment and along the study.
	4. Patients who experienced severe depression or suicide attempt in the last 5 years.
	5. Severe untreated or under-treated psychiatric illness such as active suicidal ideation or behavior (BDI-21 item #9 >0 and active suicidal ideation in C-SSRS) or depression at screening and/or initiation visit (BDI-21 items total score >30); although patients taking authorized antidepressant therapy at a stable dose for at least 2 months and stabilized can be enrolled.
	6. Patients with a history of, or current, hypotension (SBP <110 mmHg), bradycardia (HR <50 bpm), or orthostatic hypotension as defined by the European Society of Hypertension (reduction in SBP ≥20 mmHg or in DBP ≥10 mmHg).
	7. Patients with hypertension already treated with more than 2 antihypertensive drugs.
	8. Other active clinically significant illness, including unstable cardiovascular disease, angina pectoris, congestive heart failure, pulmonary hypertension, peripheral arterial disease, history of pheochromocytoma, asthma, COPD, diabetic ketoacidosis or metabolic acidosis, or neoplastic pathology, which could interfere with the study conduct, or counter-indicate the study treatment, or to place the patient at risk during the trial, or compromise their study participation.
	9. Any significant serious abnormality in the electrocardiogram (ECG), e.g. recent myocardial infarction, significant sinus bradycardia (<50 bpm), atrioventricular block (grades I to III with PR >240msec), sinoatrial block, atrial sinus disease or prolonged QTc interval at screening (ECG

Bazett's corrected QT interval (QT  $/\sqrt{[HR/60]}$  >450 msec for males or >470 msec for females), or a known history of long QTc syndrome.

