#### 5.2. EXCLUSION CRITERIA

Patients are excluded from the study if any of the following criteria apply:

- 1. Onset of HD symptoms prior to age of 21 years, corresponding to juvenile forms of HD.
- 2. HD patients presenting rigid akinesia.
- 3. Use of other vesicular monoamine transporter type 2 (VMAT2) inhibitors such as tetrabenazine, deutetrabenazine, or valbenazine within 3 months before enrollment, and at any time during the study period; and use of other antichoreic treatment such as any neuroleptic within 2 months or amantadine, memantine, riluzole within 1 month before enrollment and along the study.
- 4. Patients who experienced severe depression or suicide attempt in the last 5 years.
- 5. Severe untreated or under-treated psychiatric illness such as active suicidal ideation or behavior (BDI-21 item #9 >0 and active suicidal ideation in C-SSRS) or depression at screening or baseline (BDI-21 items total score >30); although patients taking authorized antidepressant therapy at a stable dose for at least 2 months and stabilized can be enrolled.

- 6. Patients with a history of, or current, hypotension (SBP <110 mmHg) or bradycardia (HR <50 bpm), and patients with known orthostatic hypotension as defined by the European Society of Hypertension (reduction in SBP ≥20 mmHg or in DBP ≥10 mmHg).
- 7. Patients with hypertension already treated with more than 2 antihypertensive drugs.
- 8. Other active clinically significant illness, including unstable cardiovascular disease, angina pectoris, congestive heart failure, pulmonary hypertension, peripheral arterial disease, history of pheochromocytoma, asthma, COPD, diabetic ketoacidosis or metabolic acidosis, or neoplastic pathology, which could interfere with the study conduct, or counter-indicate the study treatment, or to place the patient at risk during the trial, or compromise their study participation.
- 9. Any significant serious abnormality in the electrocardiogram (ECG), e.g. recent myocardial infarction, severe sinus bradycardia (<50 bpm), atrioventricular block (grades I to III, with PR >240 msec), sinoatrial block, atrial sinus disease or prolonged QTc interval at screening (ECG Bazett's corrected QT interval (QT /√ [HR/60] >450 msec for males or >470 msec for females), or a known history of long QTc syndrome.

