# 5.7. PATIENT WITHDRAWAL CRITERIA

In accordance with the Declaration of Helsinki, patients will be free to withdraw from the study at any time if they wish to do so, for any reason specified or unspecified. Such withdrawal should not affect the required and provided medical care.

In addition, the Investigator may interrupt the patient participation from the study at any time if he/she considers it necessary for any reason including:

- Pregnancy.
- Ineligibility (either arising during the study or retrospective having been overlooked at screening).
- Significant protocol deviation.
- Significant non-compliance with treatment regimen or study requirements.
- An AE which requires discontinuation of the study medication or results in inability to continue to comply with study procedures, particularly if the patient presents a **severe depression** (BDI-21 item total score ≥30), or **suicidal ideation or behavior** (BDI-21 Item #9 >0 and active suicidal ideation in C-SSRS), or **severe hypotension** (SPB/DBP <90/60 mmHg), or **orthostatic hypotension** as defined by the ESH, or **sustained un-tolerated bradycardia** (HR <50 bpm).
- Consent withdrawn.
- Lost to follow-up.
- The Investigator or Sponsor determines it is in the best interest of the subject to discontinue the patient's participation in the study.

Patients who discontinue study treatment or active participation in the study will no longer receive study treatment but will be followed for safety. When a patient withdraws from the study, the reason(s) for withdrawal shall be recorded by the Investigator on the relevant page of the eCRF. Whenever possible, all patients who discontinue study treatment or withdraw from the study prematurely will undergo all end-of-treatment assessments. Patients who fail to return for final assessments will be contacted by the site staff. Following a minimum of 2 documented unsuccessful telephone calls, a registered letter will be sent to the patient in a final attempt to ensure protocol compliance.

It is vital to obtain follow-up data on any patient withdrawn because of an AE or SAE. In every case, efforts must be made to undertake protocol-specified, safety, follow-up procedures.

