#### Obtaining the Patient informed consent

If a patient is eligible to be enrolled in the study, prior to conduct of any study-specific screening procedures, the Investigator, or designee, will explain to the patient the study procedures, including the risks involved and the fact that its participation is voluntary.

The Investigator should give to the patient the study's IRB/IEC-approved written informed consent form (ICF) and orally present all necessary information to the patient, in order to enable him/her to make an informed and unconstrained decision about participating in the study. An appropriately

signed ICF will be obtained prior to entry into the study for each patient who has made the decision to participate. Information regarding the collection of the patient informed consent should be registered in the source document (date, protocol number, and name of the Investigator or sub-investigator who has informed the patient).

In addition, the following assessments must be performed at Visit 0, and information must be collected and documented in the CRF within the screening period:

- Patient medical history and history of HD diagnosis, with documented genetic diagnosis;
- Patient history of all the treatments must be notified in the source documentation prior to randomization (with regimen, duration, and complications and their treatments);
- Demographics characteristics (age, gender, and ethnic origin);
- Physical and neurological examinations with the presence of chorea symptoms;
- Vital signs (SBP, DBP, orthostatic BP, and heart rate measured according to the standardized method described in section 7.3.3), body height and weight;
- List of current concomitant medications;
- Clinical scores and functional tests: UHDRS®-Motor part (including TMS and TMC, gait and dystonia sub-scores), UHDRS®-Total Functional Capacity, UHDRS®-Functional assessment, and C-SSRS, BDI, and ESS;
- 12-lead ECG (sent for centralized reading by a cardiologist);
- Safety laboratory tests (chemistry, hematology) analyzed by local laboratory (including a pregnancy test if female of childbearing potential).

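### Exclusion criterion 6 sets two different rules for orthostatic hypotension, so the plan does not settle eligibility when a qualifying drop is first measured at Visit 0 or Visit 1.

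*Protocol*

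**What the plan says.** Criterion 6 appears twice in the protocol.

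- **Synopsis (section 1.1):** "Patients with a history of, or current, hypotension (SBP <110 mmHg), bradycardia (HR <50 bpm), or orthostatic hypotension". The opening qualifier covers all three conditions.
- **Section 5.2:** past or current status is required for hypotension and bradycardia. Here the orthostatic condition is a separate limb with its own qualifier, *known*: "patients with known orthostatic hypotension as defined by the European Society of Hypertension".

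Both texts use the same thresholds: "reduction in SBP ≥20 mmHg or in DBP ≥10 mmHg".

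Screening procedures in section 8.1.1 include "Vital signs (SBP, DBP, orthostatic BP, and heart rate measured according to the standardized method". Section 8.1.2 repeats the orthostatic measurement at Visit 1 and requires all eligibility criteria to be checked again before randomization. Section 2.2.1 says the supine and standing readings are there to detect orthostatic hypotension.

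Section 2.2.3 names orthostatic hypotension as a potential side effect of the beta-blockade. When it then lists who is excluded at screening, it mentions only hypotension and bradycardia.

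SAP section 2.3 makes any violation of an entry criterion a potential reason for exclusion from the per-protocol population. SAP section 3.5 leaves that decision to the blinded data review meeting. The SAP does not restate the exclusion criteria.

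**The concern.** Two passages that both present themselves as the eligibility rule differ in the one word that decides a foreseeable case: a patient with no recorded orthostatic hypotension whose pressure drops past the threshold when measured for the study. The protocol schedules the test that finds such patients before randomization, then gives two answers about what to do with the result.

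Two things are at stake.

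- **Entry.** Sites working from different parts of the protocol can admit different patients. The risk is one the protocol singles out: the secondary objectives give particular attention to cardiovascular hemodynamic parameters, and the synopsis lists hypotension among the most frequent events in the earlier Huntington's disease trial.
- **Classification.** The blinded review must decide whether such a patient violated an entry criterion. The answer depends on which text is used. It feeds the per-protocol repeat of the primary analysis (Sensitivity #3 in SAP section 4.7.1), the other per-protocol analyses, and the reporting of significant eligibility deviations under protocol section 11.5.

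**Working it through.** No formula or stated figure bears on this point, so the check is a comparison of texts.

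**Step 1: isolate the difference.** The conditions and thresholds are the same in both places. Only the qualifier on orthostatic hypotension differs: past or current in the synopsis, *known* in section 5.2. Section 5.2 uses *current* and *known* in the same sentence for different conditions, so the ordinary reading is that they mean different things.

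**Step 2: look for a text that settles it.** *Known* is not defined in the protocol, and neither document ranks the synopsis against the body. Section 2.2.3 does not help, because its list of screening exclusions omits the orthostatic condition.

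**Step 3: apply both texts to the possible patients.**

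| Patient before randomization | Synopsis criterion 6 | Section 5.2 criterion 6, ordinary reading | Section 5.2 criterion 6, broad reading of *known* |
|---|---|---|---|
| Diagnosed before the study, drop still present | Excluded | Excluded | Excluded |
| No history, qualifying drop first measured at Visit 0 | Excluded | Not excluded | Excluded at the Visit 1 re-check, because the drop is now on record |
| No history, qualifying drop first measured at Visit 1 | Excluded | Not excluded | Arguably excluded, because section 7.3.3 puts vital signs at the start of the visit |
| No history, no drop | Not excluded | Not excluded | Not excluded |

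The texts disagree in the second and third rows under the ordinary reading. They agree only if a site adopts the broad reading, which the protocol does not state.

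**Step 4: check whether the case can occur.** It can. Sections 8.1.1 and 8.1.2 schedule the measurement at both visits, and section 7.3.3 specifies supine readings followed by standing readings at 1 and 3 minutes.

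**Step 5: check the downstream use.**

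- SAP section 2.3 refers to a violation of any entry criterion without saying which text defines it.
- SAP section 4.10.2 tabulates the incidence of a drop at the same thresholds, with no stated restriction to, or flag for, patients who already had one at Visit 1.
- Vital-sign values and changes are also summarized by position and treatment group, with Visit 1 as baseline (SAP section 4.1.1), so group-level differences at baseline can be seen there.

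**The case against.** **The broad reading of *known*.** A drop recorded at Visit 0 can fairly be called known by the Visit 1 re-check, and the thresholds attached to the term suggest that a measurement counts. This stands as a possible reading, so it is too strong to say that section 5.2 plainly admits these patients. It does not remove the problem: one site may read the word this way and another may not, and a drop first seen at Visit 1 fits the reading less easily.

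**Other screens.** Section 7.3.3 calls such a drop abnormal, criteria 8 and 10 allow exclusion on judgment, and section 4.1 expects medically stable patients. These may catch some cases. They are discretionary, and criterion 10 refers to the physical examination and laboratory results, while vital signs are a separate assessment. They do not replace a common rule.

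**Loose copying.** Criterion 9 also varies between the two places, calling sinus bradycardia significant in one and severe in the other. There the same heart-rate limit fixes the meaning. In criterion 6 the shared thresholds do not, because the difference lies in whether a new finding counts.

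**Stronger readings the documents do not support.**

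- A reader might infer that such a patient enters already meeting a withdrawal criterion. Section 5.7 says the investigator may end participation, and lists orthostatic hypotension under "An AE which requires discontinuation of the study medication or results in inability to continue to comply with study procedures". Section 7.4.1.1 defines an adverse event as something that appears or worsens during observation. An unchanged drop present before dosing does not by itself meet that condition.
- A reader might then infer added missing primary data. That depends on the same misreading of section 5.7.
- A reader might multiply an assumed prevalence by the 129 planned patients. The documents give nothing to anchor such a prevalence.

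**Conclusion.** The inconsistency is real and should be corrected. Under the synopsis, a qualifying drop first measured at Visit 0 or Visit 1 excludes the patient. Under the ordinary reading of section 5.2, criterion 6 does not. This rests on giving *known* its usual sense of already established, and on the absence of any text that defines it or gives one section precedence.

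The consequence is limited to uneven entry decisions on a named safety risk and an undefined violation status at the blinded review. How many patients this touches cannot be derived from the documents. Sample size and primary analysis method are unaffected. Because the drop precedes randomization, it is not expected to favor any arm.

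**What to change.** Reconcile criterion 6 in the synopsis and section 5.2, and align the list of screening exclusions in section 2.2.3, so that one wording states how a drop first measured at Visit 0 or Visit 1 is handled. Which rule to adopt is a clinical decision for the sponsor.

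Record the same wording in the rules for the blinded data review, so that eligibility violations are classified uniformly for the per-protocol population. If enrollment is already complete, this part can still be done before database lock with data already collected.

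Optionally, flag in the existing orthostatic-drop table of SAP section 4.10.2 those patients who already had a drop at Visit 1. This helps interpretation but is not needed to remove the contradiction.

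The cost is a wording amendment in three places and one line in the data review rules. The optional flag needs no new data.

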## 7.3.4. Electrocardiograms (ECGs)

ECG will be performed according to the AHA/ACC recommendations for the standardization and interpretation of the ECG. All ECGs will be performed after at least 5 minutes' rest in a supine or semi-supine position. 12-lead ECGs to assess safety will be recorded at Screening Visit, inclusion visit (Visit 1), Visit 2, Visit 4, and Visit 6.

All ECG will be transferred by telemetry to the ECG central reading lab (Banook cardiabase) and ECG parameters (PR, QRS, QT, and QTcF) will be registered in the database and analyzed by a cardiologist. A report will be sent to the site within 48 hours after the visit. One paper version will be edited for the source document that can be examined by the Investigator during the visit.

At the inclusion, the ECG will be triplicated i.e. 3 successive records at 5 minutes of intervals and the average of all parameters will be calculated for baseline reference. This allows to have good quality for the reference ECG. Then the measurements of the 3 ECGs are averaged in a report.

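### Exclusion 9 names Bazett's correction but prints its inverse, so its words and its formula can give opposite eligibility decisions for the same ECG

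*Protocol*

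**What the plan says.** Exclusion 9 in Protocol section 5.2 lists ECG abnormalities that bar entry. One of them is a "prolonged QTc interval at screening", defined by the limit "Bazett's corrected QT interval (QT /√ [HR/60] >450 msec for males or >470 msec for females". The synopsis (Protocol 1.1) gives the same criterion with the same expression, HR over 60 under a root in the denominator, and continues "msec for males or >470 msec for females), or a known history of long QTc syndrome". No other place in the protocol or SAP gives a QTc formula.

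Three other provisions bear on the point:

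- The same exclusion separately bars "severe sinus bradycardia (<50 bpm"; exclusion 6 also bars heart rates below 50 bpm.
- Protocol 7.3.4 sends all ECGs to a central reader and states that "ECG parameters (PR, QRS, QT, and QTcF) will be registered in the database". A cardiologist analyses them, a report reaches the site within 48 hours, and the investigator has a paper copy at the visit. Bazett's QTc is not in the list.
- SAP 2.3 makes a breach of any eligibility criterion a possible ground for removal from the Per Protocol population, decided at the blinded data review.

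**The concern.** The criterion states one numeric limit in two ways, by the name of a correction and by a formula, and the two are not the same quantity. QT shortens as heart rate rises, so a rate correction has to raise QT above 60 bpm and lower it below 60 bpm. The printed expression does the opposite. Two sites reading the same sentence, one following the name and one following the formula, could reach opposite decisions on the same tracing.

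At stake is a cardiac entry safeguard in a trial of a beta-blocker whose safety objective singles out cardiovascular parameters. There is also an analysis consequence. Who counts as an exclusion-9 deviation depends on which reading the data review adopts. That feeds into the Per Protocol population, which is used for Sensitivity #3 and for the repeat analysis of the key secondary endpoint (SAP 4.7.1 and 4.7.2).

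**Working it through.** **Inputs.** From the protocol: the printed expression QT/√(HR/60), the limits of 450 ms (men) and 470 ms (women), and the entry floor of 50 bpm. From the standard definition of the named method: Bazett QTc = QT/√RR, with RR in seconds. The documents contain no ECG data, so the QT and heart-rate pairs below are illustrative assumptions.

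**Step 1, algebra.** RR = 60/HR, so

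- Bazett: QT/√(60/HR) = QT × √(HR/60)
- As printed: QT/√(HR/60)
- Printed ÷ Bazett = 1/(HR/60) = 60/HR

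The ratio does not depend on QT, so it holds for every patient.

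**Step 2, where the limit falls.** The uncorrected QT at which a patient reaches the limit L is L × √(HR/60) as printed and L/√(HR/60) under Bazett. The Bazett value of a patient sitting exactly at the printed limit is L × HR/60.

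| HR (bpm) | Printed ÷ Bazett | QT limit as printed, M/F (ms) | QT limit under Bazett, M/F (ms) | Bazett QTc at the printed limit, M/F (ms) |
|---|---|---|---|---|
| 50 | 1.200 | 411/429 | 493/515 | 375/392 |
| 60 | 1.000 | 450/470 | 450/470 | 450/470 |
| 70 | 0.857 | 486/508 | 417/435 | 525/548 |
| 80 | 0.750 | 520/543 | 390/407 | 600/627 |
| 90 | 0.667 | 551/576 | 367/384 | 675/705 |

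Under Bazett the permitted uncorrected QT falls as the rate rises; as printed it climbs.

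**Step 3, single tracings.**

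| Patient | √(HR/60) | As printed | Bazett | Decision as printed / by name |
|---|---|---|---|---|
| Man, HR 80, QT 400 | 1.1547 | 400/1.1547 = 346 | 400 × 1.1547 = 462 | passes / excluded |
| Man, HR 75, QT 410 | 1.1180 | 367 | 458 | passes / excluded |
| Woman, HR 80, QT 420 | 1.1547 | 364 | 485 | passes / excluded |
| Man, HR 52, QT 425 | 0.9309 | 425/0.9309 = 457 | 425 × 0.9309 = 396 | excluded / passes |

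The slow-rate error acts only from 50 to below 60 bpm, because lower rates are barred anyway. The fast-rate error covers every rate above 60 bpm.

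**Step 4, can it be checked afterwards?** Heart rate is not in the 7.3.4 list of registered ECG parameters, but QT and QTcF are. Fridericia's correction is QTcF = QT/RR^(1/3), so RR = (QT/QTcF)³. Take QT 400 ms at 80 bpm: RR = 0.75 s and QTcF = 440 ms to the nearest millisecond. Working back, RR = (400/440)³ = 0.751 s. This gives Bazett 400/√0.751 = 462 ms and the printed form 400 × √0.751 = 347 ms, against 462 and 346 directly. Rounding costs about 1 ms.

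**The case against.** The strongest reply is that a wrong expression in brackets need not have affected anyone. The correction is named beside it. Many sites may read a Bazett value from the ECG device, and those that do are unaffected. The central cardiologist reviews the Visit 0 tracing, and the QTc limit is only one example in an open-ended list of serious ECG abnormalities. A man with a Bazett QTc near 600 ms at 80 bpm could therefore be stopped by other parts of the same criterion. All of that stands as a limit on the consequence. It does not make the name and the formula agree, and nothing in the documents tells a site which to follow.

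Two stronger readings are tempting and should not be drawn.

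- A reader might infer that sites must calculate the value by hand with the printed formula, because the central list contains only QTcF. Section 7.3.4 describes what is registered in the database. It does not say that this is everything in the report to the site, and it does not exclude a device value.
- A reader might infer that the entry QTc cannot be compared with QTcF on study. No such comparison is planned: SAP 4.1.1 takes the ECG baseline from Visit 1, and section 7.3.4 registers QTcF for all ECGs, screening included. Using one correction at entry and another on study is not in itself an error.

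A PDF reading fault is an unlikely explanation. The synopsis and section 5.2 were extracted in different forms and show the same expression.

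**Conclusion.** The point holds in this form: exclusion 9 contradicts itself in both places where it appears. Relative to the correction it names, the printed formula is wrong by the factor 60/HR: 20% too high at 50 bpm, 25% too low at 80 bpm and 33% too low at 90 bpm. Any misclassification is conditional on someone having applied the printed formula. The documents do not show that anyone did, and they do not say whether a device, the central reader or a hand calculation supplies the value. They therefore support no count of affected patients.

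The primary endpoint, the power and the mITT analysis model are untouched. The reach into the analysis is limited to possible eligibility deviations and so to Per Protocol membership. The size of the formula error rests only on the standard definition of Bazett's correction. Which correction and which limit ought to govern entry is a clinical decision on which this point takes no position.

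**What to change.** 1. Reconcile the named correction and the printed formula in the synopsis and in section 5.2, so that both express one quantity.
2. State in the protocol which source supplies the screening QTc for this criterion, given that section 7.3.4 lists QTcF as the registered corrected value.
3. From the stored Visit 0 ECG data, derive the QTc both under the named correction and as printed. Use RR from the ECG heart rate if it is held, otherwise (QT/QTcF)³. List every patient for whom the two give different decisions.
4. Bring randomised patients on that list to the blinded data review before database lock as possible exclusion-9 deviations, judged under the reconciled definition. Where the ECG is held, check screen failures rejected for QTc at 50 to below 60 bpm in the same way.

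The SAP was finalised in July 2024, while the protocol planned a one-year study starting in late 2021. The text correction may therefore come too late to change screening; the documents do not give enrolment status. Steps 3 and 4 remain useful for as long as the database is open.

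The cost is a text correction in two places, a sentence on the source of the value, and a small derivation on data already collected. No new measurement is needed. The main side effect may be a few more listed eligibility deviations and, depending on the review, a slightly smaller Per Protocol population.
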